4.2 Exclusion Criteria

Patients not meeting the inclusion criteria above will not be included in the study. No other exclusion criteria will be used.

4.3 Recruitment and retention

4.3.1 Informed consent considerations

We have received a waiver of informed consent and HIPAA authorization for all physician-subjects and patient-subjects in this study. The goal of this project is to improve existing decision support to reduce the use of potentially dangerous medications in the elderly, consistent with numerous professional guidelines and quality metrics. Providers will retain oversight of their patients' care and will be able to make therapeutic choices based using their professional judgement. Patients will not receive any direct intervention as a result of their inclusion in the study.

We have provided further information in Section 8.2.

4.3.2 Inclusivity of study subjects

Atrius Health

Physician and patient subjects will be included based on their meeting eligibility criteria as part of routine care, and the study population will be highly inclusive. Further, pilot data indicate that 201 primary care providers at Atrius currently meet eligibility criteria. Based on these same pilot data, the number of patients included in the analyzable population should exceed 2000 patients in Stage 1 and 4000 patients in Stage 2. Importantly, we expect these participants to cover

a broad range of participants by gender and race/ethnicity. Of these, 59.2% are female, 84.6% are White, 6.4% are Black or African American, 1.4% are Hispanic, 3.1% are Asian/Pacific Islander, 0.3% are American Indian/Native American, and 4.2% are other races or unknown. These estimates at Atrius Health are similar to the overall estimates of older adults in the U.S. Medicare population. Further, given the minimal risk nature of the study, participants will not receive incentives, remuneration, or be required to provide informed consent.

Mass General Hospital.

Physician and patient subjects will be included based on their meeting eligibility criteria as part of routine care, and the study population will be highly inclusive. As at Atrius, we expect these participants to cover a broad range of participants by gender and race/ethnicity. Given the minimal risk nature of the study, participants will not receive incentives, remuneration, or be required to provide informed consent.

5. Study Interventions

5.1 Therapeutic areas

The focus areas for the EHR tools will be primarily drawn from the outpatient Choosing Wisely recommendations in geriatric medicine but are also informed by the Beers Criteria and other major clinical guidelines.^{4,29} In specific, we plan to focus on the following therapeutic classes: (1) benzodiazepines; (2) sedative hypnotics (sleep medicines) and (3) anticholinergics.

5.2 Study interventions

Physicians in the adaptive trial randomized to one of the 15 active intervention arms will receive one of several possible enhanced EHR decision support tools to guide their care of

eligible patients when these patients come to the clinic for an appointment. Physicians in the replication trial randomized to one of the 3 active intervention arms will receive one of several possible enhanced EHR decision support to guide care. The type and timing of an alert will vary based on the intervention arm.

These EHR tools will be tested in combination or on their own in the 15 active intervention arms outlined below for the adaptive randomized trial at Atrius. The two specific EHR tools for the replication trial at MGB will be determined based on the adaptive randomized trial results:

Arm	Components included in the EHR tools							
	Alert type	Order entry (X) vs. Open encounter	Follow-up booster	Cold state outreach	Simplification	Sign-off moment	Pre-commitment	Framing: Guideline risks
1	Enhanced	X						
2	Enhanced							
3	Enhanced	X	X					
4	Enhanced		X					
5	Enhanced	X		X				
6	Enhanced			X				
7	Enhanced	X			X			
8	Enhanced				X			
9	Enhanced	X				X		
10	Enhanced					X		
11	Enhanced	X					X	
12	Enhanced						X	
13	Enhanced	X						X
14	Enhanced							X
15	Basic	X						
16	None							

Arms 1 through 14 are enhanced EHR tools to encourage the deprescribing of the medications under study. Arm 15 is a basic EHR alert that is meant to represent the type of clinical decision support that is commonly given to providers – without enhancements using behavioral science principles (if any decision support is provided). Physicians randomized to usual care (Arm 16) will receive no intervention.

The central component of arms 1 through 14 will be an enhanced EHR alert (known as a Best Practice Advisory [BPA]). The enhanced BPA will appear on each provider's EHR screen and will contain several standard components. The BPA will:

1. give providers information about why the medication is dangerous for their patient using the behavioral science principle of salience to make this information as impactful as possible;
2. include a set of tips to help providers discuss medication discontinuation with their patients;
3. ask providers to select an acknowledgment reason if they decided not to discontinue the medication;
4. include a SmartSet order set that will allow providers to order a gradual dose taper for their patient, which limits risks of withdrawal symptoms for the patients for benzodiazepines and sedative hypnotics, order alternative medications, place a referral to a behavioral health specialist, provide instructions on how to make lifestyle modifications to improve patient symptoms, and add customizable patient instructions for how to gradually taper off benzodiazepines and sedative hypnotics, as applicable.

The BPA will display either when the provider orders a medication (Order Entry) or opens the chart (Open Encounter) for eligible patients, depending on the arm. In specific, the enhanced BPA will fire at Order Entry in Arms 1, 3, 5, 7, 9, 11, 13 and 15; the enhanced BPA will fire at Open Encounter in Arms 2, 4, 6, 8, 10, 12 and 14.

We will also test several other modifications to this enhanced BPA. In specific, as outlined in the table above, we will add in a boosting option in the enhanced BPA in Arms 3 and 4, which is a provider-directed option for a follow-up in-basket message sent 4 weeks after the BPA is triggered. In Arms 5 and 6, we will incorporate a prior, “cold state” outreach component, consisting of an in-basket message sent to the eligible provider 2 days before the

eligible patient is scheduled for an in-person or telehealth visit. Arms 7 and 8 will test simplified language of the BPA. Arms 9 and 10 will test the addition of a BPA at medication sign-off for providers. Arms 11 and 12 will test the use of a two-staged pre-commitment BPA in which the providers are prompted to discuss risks of these high-risk medications and share a handout about the risks with their patients, at their own discretion. Arms 13 and 14 will test the framing of different risks of the high-risk medications in the BPA.

If patients are eligible for alerts to be fired for multiple therapeutic classes of interest (e.g., benzodiazepines and sedative hypnotics), the EHR tools will appear for both classes separately.

5.3 Measures to minimize bias: randomization and blinding

Providers will be randomized to treatment arms in equal proportions based on blocks. We will use provider-based cluster randomization to minimize the possibility of contamination in study interventions between practices and clinic staff. For the randomization, we will use stratified randomization based on clinic practice size and baseline rates of prescribing to reduce potential imbalances between the providers assigned to the treatment arms.

The providers will not be blinded to which arm they were assigned to, as blinding is the context of an intervention that is intended to motivate action will be infeasible. The study statistician, in partnership with data analysts at Atrius Health, will generate and implement the randomization scheme, with oversight by the Principal Investigators. Investigators will be blinded to the treatment arms during interim and final analyses.

6. Study Assessments and Procedures

6.1 Baseline data

We will collect baseline data on patients and providers using extracted EHR data and/or administrative claims data as applicable for the study aim. This baseline data will be used to assess any potential imbalances in the characteristics of providers or patients despite randomization. The baseline data will include, but are not limited to: gender, rural/urban practice setting, baseline rates of prescribing, practice location, and patient case-mix. We will also collect patient data that include but are not limited to: sociodemographic data, medical history and comorbidities, baseline resource utilization in prior 12 months (i.e., number of visits), biometric values (e.g., serum creatinine, systolic/diastolic blood pressures).

6.2 Outcomes

For both Stages, the primary outcome will be a binary composite measure of a reduction in inappropriate prescribing, evaluated using EHR data from Atrius Health. In specific, we will measure a composite of 1) discontinuation of high-risk medications (benzodiazepines, sedative hypnotics, or anticholinergics [included in secondary analyses]), defined by either: a) active discontinuation and no subsequent order or b) no order during follow-up or 2) ordering a gradual dose taper (for benzodiazepine or sedative hypnotics). If either of these actions is taken by the provider for a specific patient at any point in the follow-up window, we will classify the patient as having had a reduction in inappropriate prescribing. If the patient has multiple therapeutic classes of interest (e.g., benzodiazepines and sedative hypnotics), we will classify patients with a reduction for any class as a “reduction” for the composite measure. In secondary analyses, we will include anticholinergics. We will also stratify patients by their number of eligible therapeutic classes (i.e., one, two, or three classes) and analyze outcomes within these strata.

In Stage 2 and the replication trial, secondary outcomes include the quantity of high-risk medication prescribed, defined by number of milligram equivalents of high-risk medications prescribed to patients in the follow-up period to capture cumulative prescribing by all providers

at Atrius Health. As above, we will also stratify patients by their number of eligible therapeutic classes (i.e., one, two, or three classes) and analyze outcomes within these strata.

In Stage 2 and the replication trial, tertiary outcomes will include the extent to which medications are filled and consumed by patients, as measured within the subgroup of patients with claims data. In specific, these outcomes will be conducted among the large subgroup of patients funded by Medicare, including pharmacy claims via the secure MedRIC data enclave. In particular, we will measure the quantity of high-risk medication dispensed, defined by number of milligram equivalents of high-risk medications filled by patients, in follow-up, using pharmacy claims data. Other tertiary outcomes will include the occurrence of clinically-significant adverse drug events, including but not limited to, sedation or cognitive impairment, and all-cause hospitalizations and falls or fractures, measured in administrative claims data. These clinical outcomes will be evaluated using validated and CMS-driven ICD-10-CM diagnosis and procedure-based algorithms applied to these patients' medical and pharmacy administrative claims data. Because the sensitivity of clinical outcomes in EHR systems is known to be low (e.g., because patients may seek subsequent care at other healthcare systems), using routinely-collected data from insurers overcomes this limitation.³⁰ We will also evaluate implementation of the intervention using structured deidentified data from the EHR about use of the EHR system, which will help inform how to scale the interventions (see Data to be collected form).

At the conclusion of the trial, a brief optional survey will be administered electronically to providers who were included in the trial (see “Provider outreach email” and “Provider survey” in attachments). The purpose of the survey is to understand providers' satisfaction with the decision support and what modifications they would recommend in the future. These findings will be used to help understand implementation of the decision support and potential for scalability to other settings. The surveys will be prepared in MGB REDCap and delivered by secure email from the Atrius Site PI and will be completely optional. The survey will collect

provider email addresses for remuneration purposes and will otherwise not collect any HIPAA identifiable information or information about patients. The study-specific provider identifier and email address will be the only identifiers, necessary for the evaluation of implementation and remuneration. Their servers are protected by the same firewall systems as other data. Non-respondents will receive a second reminder email but otherwise receive no outreach. At the end of the survey, providers will be offered a \$25 gift card for completing the survey, in which those who opt-in to receive remuneration will provide an email address. MGB study staff will receive email addresses via REDCap and will send a gift card code to the email address provided but otherwise will not interact with providers. Providers are not obligated to complete the survey in any way or to provide their email.

After the administration of the optional survey, Atrius providers included in the trial will be invited to participate in a one-time optional qualitative interview (lasting about 20-30 minutes). The purpose of the interviews is to complement the surveys and understand barriers faced by providers in deprescribing, how to improve the decision support, and how interested they would be in sustaining or building upon the interventions. Providers will be invited to participate via email delivered by Atrius study staff (see “Provider interview outreach email”) based on physician factors, and if interested, they will be invited to contact [name], the MGB investigator trained in qualitative methods who will conduct the interview; by doing so, they will have provided implied consent to have their name shared only with the MGB investigator, but otherwise there will be no other HIPAA identifiable information shared outside of Atrius. Other MGB staff or external individual will not have access; the provider will otherwise only be assigned a study identifier for the purpose of interview analysis. The interviews will not collect any HIPAA identifiable information about patients. Before proceeding with the interview, verbal consent will be obtained by [name]. The interview will be conducted using a semi-structured interview guide (see “Provider interview guide”). Providers will be offered \$100 for participating in the interview, administered by MGB study staff. In order

to receive remuneration for interview participation, Atrius providers will provide [name] with a mailing address and social security number to process a check per MGB remuneration policy. This information will only be used for payment purposes and will be destroyed after study payments are complete. All interviews will also take place through Zoom, a secure MGB-approved platform, with audio recording, and the data will be securely stored like all other study data. We will use immersion-crystallization methods for data analysis. We will follow all established standards for qualitative research. In total, we plan to invite approximately 50 providers with a sampling across the study arms, to conduct interviews with between 10-20 providers, depending on response rate and thematic saturation. Providers are not obligated to participate in the interview in any way.

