3.6 End-of-study definition

The adaptive trial will be completed approximately 8 months after Stage 2 randomization. Providers and their eligible patients will be followed until the end of this follow-up date, or until censoring.

The replication trial will be completed 12 months after randomization. Providers and their eligible patients will be followed until the end of this follow-up date, or until censoring.

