Because this is a randomized trial, our primary analyses are planned as unadjusted; in secondary analyses, we will adjust for patient age, race/ethnicity, and gender.. Given the nature of the data and how the outcomes are categorized, there will not be missing values for the primary endpoint, as the absence of action is classified as no action by the provider. For the primary analysis, we will include all eligible patients in the denominator who had at least one in-person or telehealth visit with their primary care provider. In secondary analyses, we will

include all eligible patients of those primary care providers in the denominator, regardless of whether the patient visited the provider over the follow-up period.

7.3.1b Replication trial

All analyses will use intention-to-treat principles. We will use generalized estimating equations to adjust for clustering and repeated observations. For the inappropriate prescribing outcome, we will use a log link function and binary distributed errors. For the adverse clinical outcomes, we will use a log link function and binary distributed errors. These models generate the estimated relative risks (RRs) with robust standard errors and are considered to be particularly appropriate when outcomes are common (e.g., incidences of $\geq 10\%$). Because this is a randomized trial, our primary analyses are planned as unadjusted; however, in secondary analyses, we will adjust for patient age, race/ethnicity, and gender.

Given the nature of the data and how the outcomes are categorized, there will not be missing values for the primary endpoint, as the absence of action is classified as no action by the provider. For the primary analysis, we will include all eligible patients in the denominator who had at least one visit with their primary care provider. In secondary analyses, we will include all eligible patients of those primary care providers in the denominator, regardless of whether the patient visited the provider over the follow-up period.

7.3.2 *Analysis of secondary endpoints*

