For the secondary outcome of cumulative medication prescribing, will use an identity link function and normally distributed errors within the generalized linear models. For tertiary adverse clinical outcomes and resource utilization outcomes, we will use a log link function and binary distributed errors within the overall multivariable models. These models generate the estimated relative risks (RRs) with robust standard errors and are considered to be particularly appropriate when outcomes are common (e.g., incidences of $\geq 10\%$). For these outcomes from claims data, we will follow patients whose providers are randomized to the study from the time

of randomization until they are censored due to loss of continuous enrollment in their health plan or leaving Atrius Health. Due to the nature of the randomization, we do not anticipate any systematic differences in the amount of follow-up time per arm but will account for any imbalances using inverse probability censoring weights.

Because this is a randomized trial, our primary analyses are planned as unadjusted; however, if there are strong patient-level predictors of the outcomes not balanced by stratified randomization, we will adjust for these in the primary analyses. Given the nature of the data and how the outcomes are being measured, there should not be missing values. However, should there be sufficient missing data (e.g., >10%), we will use multiple imputation.³¹

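### The primary endpoint credits absence of an order as deprescribing without requiring observation to the end of follow-up, so some patients who die or leave count as successes

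*Combined protocol and SAP*

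**What the plan says.** Section 6.2 makes the primary outcome a binary composite of discontinuation or an ordered taper. Discontinuation is met by "a) active discontinuation and no subsequent order or b) no order during follow-up". The scoring sentence then reads "If either of these actions is taken by the provider for a specific patient at any point in the follow-up window", in which case the patient counts as a reduction.

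The provisions that bear on who must be observed, and for how long, are these:

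- 7.3.1a, primary denominator: eligible patients "who had at least one in-person or telehealth visit with their primary care provider". Section 7.3.1b likewise asks for at least one visit.
- 7.3.1a and 7.3.1b, secondary denominator: all eligible patients, "regardless of whether the patient visited the provider over the follow-up period".
- 4.2, after the inclusion criteria: "No other exclusion criteria will be used".
- 7.3.1a and 7.3.1b, missing data: "there will not be missing values for the primary endpoint, as the absence of action is classified as no action by the provider".
- 3.6: "Providers and their eligible patients will be followed until the end of this follow-up date, or until censoring". Censoring is not defined there.
- 7.3.2: censoring at loss of plan enrolment or departure from Atrius, with inverse-probability weights, introduced by "For these outcomes from claims data". Death is not named.

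**The concern.** Limb (b) is met when nothing happens. For a patient under continuous care, no order over the whole window is reasonable evidence that the drug was stopped. For a patient who died or moved to another practice, an empty order record says only that this practice had no further chance to prescribe. The rule treats the two alike. Limb (a) has the same gap: after an active discontinuation, the absence of a later order is informative only while the patient is still there to receive one.

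The population is aged 65 or more, and follow-up runs to at least 8 months in Stage 2, so some deaths and departures are to be expected. The planned effect in the adaptive trial is a fraction of a percentage point, so even a small number of such patients falling unevenly between groups is of the same order as the effect sought.

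**Working it through.** **Step 1. Follow one patient through the rules.** An eligible patient attends one visit, receives no order for the study drug in follow-up, and dies or leaves two months later.

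- The visit puts the patient in the primary denominator, and 4.2 gives no ground for exclusion.
- No order was written in follow-up, so limb (b) of 6.2 is met and the patient is a success.
- 3.6 allows for censoring but states no consequence for this endpoint. The events and weights in 7.3.2 are limited to claims outcomes.
- The multiple imputation in 7.3.2 is not triggered, because the patient already has a value.

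No provision changes the score.

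**Step 2. Ask whether 7.3.1 supplies the missing rule.** It says absence of action is classified as no action. Two readings are open. If action has the meaning used in 6.2, where discontinuation (limb (b) included) is one of the actions, absence of action means that orders continued and no taper was ordered; the patient above stays a success. If action means something the provider actively did, the patient had none and is not a success. The text does not choose, and it mentions neither death nor departure.

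**Step 3. A yardstick for the adaptive trial.** Inputs from 7.2: composite rate 5%, odds ratio 1.15.

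- Planned active rate: odds 0.05/0.95 × 1.15 = 0.06053; rate 0.06053/1.06053 = 0.0571. The plan therefore seeks 5.00% versus 5.71%, a difference of 0.00707, or about 7 patients per 1,000.
- The 5% is the rate of the composite, and the composite includes limb (b), so no-order losses are taken to be inside it. Let q be the share of patients who are such losses (assumption; no figure is given) and a the success rate among the rest: 0.05 = q + (1 − q)a, so a = (0.05 − q)/(1 − q).
- With no true effect, raising q by d in one group raises its rate by d(1 − a). Setting this equal to 0.00707 gives d = 0.00707/(1 − a).

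| Assumed q | a | d |
|---|---|---|
| 1% | 0.0404 | 0.0074 |
| 2% | 0.0306 | 0.0073 |
| 3% | 0.0206 | 0.0072 |

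Across this range d is about 0.7 percentage point. If the excess falls in usual care instead, the odds ratio is 1/1.15 = 0.87.

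This d counts only losses with no order. If half of all losses have no order (assumption), the excess in total death or departure would have to be 0.0072/0.5 to 0.0074/0.5, about 1.4 to 1.5 points.

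**Step 4. Compare with chance variation.** Section 3.2.1 gives about 200 providers split roughly equally; 7.2 gives 20 patients per provider and a within-provider correlation of 0.3. Design effect: 1 + 19 × 0.3 = 6.7. Effective size per group: 100 × 20/6.7 = 298.5. Standard error of the pooled difference: √(2 × 0.05 × 0.95/298.5) = 0.0178, about 1.8 points. The 0.7-point yardstick is about 0.4 of one standard error.

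**The case against.** Four arguments can be made for the plan as written.

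First, the primary analysis does have an observation condition. The one-visit rule removes patients never seen, which leaves a narrow group: seen, given no order, then lost. That is correct, and it rules out saying that there is no condition at all. But the rule says nothing about the time after the visit, and the secondary analysis drops it.

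Second, a reader might infer that 7.3.1 contradicts 6.2 outright and turns every limb (b) success into a failure. The documents do not support that. Section 6.2 itself labels discontinuation, limb (b) included, an action, so the two sections can be read together. What remains is an ambiguity. Under the harmonised reading it leaves the lost patient a success.

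Third, impact is not demonstrated. There are no loss rates, randomisation makes a large imbalance between the pooled groups unlikely, and the yardstick lies well within the standard error. All of this stands. It limits the claim to sensitivity, but does not make the scoring of a dead or departed patient correct.

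Fourth, scoring lost patients as not reduced uses post-randomisation status and misclassifies those who truly stopped. This is a real cost. The remedy does keep every patient in the denominator, and a second analysis that censors them shows how much the choice matters. The pharmacy-claims outcome in 6.2 captures some prescribing elsewhere, but it is tertiary, covers a subgroup, and leaves the primary endpoint unchanged.

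**Conclusion.** The gap is in the text and needs no assumption: under 6.2, a patient seen once, given no order and then lost to death or departure is recorded as deprescribed. No other section alters that, and limb (a) is equally open after an active discontinuation. It should be fixed before the primary analysis.

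The size is a yardstick only. About 0.7 point of excess no-order loss in one group would imitate the planned odds ratio, given the 5% and 1.15 of 7.2 and no-order losses lying inside the 5%. The direction is unknown.

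Two further inferences are not supported. One is that equal losses in all groups would dilute the planned odds ratio below 1.15: that needs such losses to come on top of the 5%, whereas 7.2 states the 5% for the composite itself. The other is a size for the replication trial: no baseline rate is given for it, and the primary-outcome paragraph of 6.2 is written for the two Stages and Atrius data, so carrying limb (b) across is itself an inference.

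**What to change.** - In 6.2, credit limb (b) only for patients alive and still with the practice at the end of follow-up.
- State one rule for patients lost without an active discontinuation or taper, for example 'not a reduction', and say how limb (a) is scored when death or departure follows an active discontinuation.
- Report the number of such patients by arm.
- Add a sensitivity analysis that censors them, extending the inverse-probability weights of 7.3.2 to this endpoint and naming the events, including whether death is one.
- Reword the missing-values sentence in 7.3.1a and 7.3.1b to agree with 6.2.

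The cost is wording in three places, light programming and one extra analysis. The observed success rate will fall by the share of patients reclassified: in the notation above, from 5% to 5% − q, or 4%, 3% or 2% at the assumed q of 1%, 2% or 3%. Some true discontinuations among lost patients will be scored as failures, which the censoring analysis checks. The change also relies on death and departure dates being available in the EHR extract, which is an assumption to confirm with the data analysts.

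### Claims-based adverse drug events and falls can count office diagnoses made by the unblinded randomised provider, so detection may differ by arm; an inpatient/emergency version should be reported beside the all-claims version.

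*Combined protocol and SAP*

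**What the plan says.** - **Outcome and tier.** Section 6.2 lists, for Stage 2 and the replication trial: "Other tertiary outcomes will include the occurrence of clinically-significant adverse drug events, including but not limited to, sedation or cognitive impairment". All-cause hospitalisations and falls or fractures stand in the same list. All are tertiary.
- **Source.** "These clinical outcomes will be evaluated using validated and CMS-driven ICD-10-CM diagnosis and procedure-based algorithms", "applied to these patients' medical and pharmacy administrative claims data". No rule is given on care setting, on who made the diagnosis, or on repeat codes.
- **Reason for using claims.** Section 6.2 notes that EHR data miss care received in other systems and says that "using routinely-collected data from insurers overcomes this limitation". It does not discuss equal detection between arms.
- **Blinding.** Section 5.3: "The providers will not be blinded to which arm they were assigned to". It adds: "Investigators will be blinded to the treatment arms during interim and final analyses".
- **Intervention.** Under Section 5.2 the enhanced alert in Arms 1 to 14 is to "give providers information about why the medication is dangerous for their patient using the behavioral science principle of salience". Arms 11 and 12 add a discretionary prompt to talk through the risks and hand over a leaflet, and Arms 13 and 14 vary how risks are framed. Under Section 3.2.1 usual care receives no tool.
- **Analysis.** Section 7.3.2 specifies a log-link model giving relative risks, with censoring weights for unequal follow-up. It plans no sensitivity analysis for detection.

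**The concern.** The randomised provider may both receive the tool and record some of the outcome. A provider reminded of a drug's risks may ask about drowsiness, confusion or falls more often, or be readier to code them, than a usual-care provider seeing the same patient. Randomisation does not protect against this, because the difference arises after assignment. A measured difference would then mix the effect on patients with the effect on recording.

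The outcome is tertiary, but it is not incidental. Section 2 includes fewer adverse drug events in the overall hypothesis, and Section 7.2 claims adequate power for them in the replication trial. Section 6.3 rules out patient-directed prospective adverse-event monitoring and relies on provider reports, so claims are the main planned between-arm comparison of clinical harm. A hidden benefit or a false harm signal there could colour the conclusion about the tools.

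**Working it through.** The plan has no figure to reproduce. Section 7.2 asserts power for adverse events without an event rate, an effect size or a number of patients. The check is therefore whether each link stands in the text, followed by an illustration of scale.

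**Links**
1. Office claims are eligible: Section 6.2 says medical claims and states no restriction. This is inferred from silence, since the algorithms themselves are not reproduced.
2. The possible coder is the randomised unit (Section 3.2) and is unblinded (Section 5.3).
3. The stimulus differs by arm: drug danger is made salient in Arms 1 to 14, and there is no tool in usual care.
4. Nothing in the plan offsets this. Validation describes an algorithm's average accuracy, not equal sensitivity between arms. Blinded investigators do not alter how providers code. Censoring weights address follow-up time.

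**Illustration (all inputs assumed; none are in the documents)**

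Let s be the share of patients counted in usual care who qualify only through the randomised provider's code, and x the relative change in such coding that the tool causes for the same events. The outcome is binary per patient, so a code for a patient who already qualifies elsewhere adds nothing. Taking s as the share of events first coded by that provider would overstate the bias. If the true risk ratio is the same for both kinds of event:

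observed RR = true RR × (1 + s·x)

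- True RR 1.00, s = 0.3, x = 10%: 1 + 0.03 = 1.03.
- True RR 1.00, s = 0.6, x = 30%: 1 + 0.18 = 1.18.
- If the tool instead lowers coding, the same inputs give 1 − 0.03 = 0.97 and 1 − 0.18 = 0.82.

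For comparison, suppose deprescribing rises by 10 points, the difference named for the replication trial in Section 7.2, and risk is halved in those patients (assumed). The true RR is about 1 − 0.10 × 0.5 = 0.95. It would be observed as 0.95 × 1.03 = 0.98 at the low end and 0.95 × 1.18 = 1.12 at the high end. Exact cancellation needs s·x = 1/0.95 − 1 = 0.053, for example s = 0.5 with x of about 11%.

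For larger true effects, the rise in the provider's coding that erases the benefit is x = (1/RR − 1)/s:

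| True RR | 1/RR − 1 | s = 0.5 | s = 0.25 |
|---|---|---|---|
| 0.80 | 0.25 | 50% | 100% |
| 0.85 | 0.18 | 35% | 71% |
| 0.90 | 0.11 | 22% | 44% |

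The bias thus matters most when the true clinical effect is small or the randomised provider supplies much of the coding. It fades as s falls.

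**The case against.** The strongest case against is that several links are inferred and the size is pure assumption. Much of this stands, and it rules out stronger readings that a reader might draw:

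- **That the tools warn about the very events counted.** The alert text is not shown. Section 5.2 says only that the drug's danger is explained. Sedation and confusion are named as study outcomes, not as alert content. The discussion tips in the alert concern stopping the drug, not its harms. The explicit risk-discussion prompt is confined to Arms 11 and 12, which may not be carried into Stage 2 or the replication trial.
- **That primary care providers enter most of these codes.** No section says so. Section 6.2 stresses care received elsewhere, which would make s smaller.
- **That the bias runs against the tools.** This is the likelier direction, but providers may also attribute fewer symptoms to a drug once it has been stopped.
- **That all claims count without limit.** The fair statement is that no limit is given here. The algorithms may contain setting rules, and the revision log mentions a supplemental analysis plan for the replication trial that cannot be identified as a separate document in the text supplied.
- **That the provider's own diagnoses should be removed, or the main definition replaced.** Section 8.1 describes scrambled provider identifiers, so matching billers to trial providers may not be simple. The order set's behavioural health referral could also generate codes from other clinicians. Making inpatient and emergency claims the main definition would drop sedation and cognitive impairment managed as outpatients and so change the question.
- **That every clinical outcome is exposed.** Fractures and all-cause hospitalisations depend little on coding discretion.

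What the objection does not remove is the gap itself: office codes from an unblinded, prompted provider are not excluded, and no planned analysis would show whether detection differed by arm.

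**Conclusion.** The point holds as a risk of differential ascertainment in the coding-sensitive tertiary outcomes: sedation, cognitive impairment, other adverse drug events and falls. It is not a demonstrated bias. It rests on two inferences: that unrestricted medical claims include office diagnoses by the randomised provider, and that making drug risks salient can alter how often that provider asks about and codes events. The range of 1.03 to 1.18 under a true null shows scale only. At its low end a true 0.95 still appears as 0.98, so cancellation or reversal is possible but not assured. The point deserves a change to the plan because the outcome is part of the stated hypothesis and the remedy is cheap.

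**What to change.** In Section 6.2:

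1. State the care-setting and coding rules of each claims algorithm.
2. For sedation, cognitive impairment, other adverse drug events and falls, pre-specify a second version restricted to inpatient and emergency department claims. Fractures and all-cause hospitalisations need none. Where falls and fractures are combined, apply the restriction to the fall component.
3. Report both versions by arm, with intervals, and say in advance that a difference in all claims which the restricted version does not show will be treated as possibly due to ascertainment.

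The third item should say possibly: the restricted version could also miss a real difference through imprecision, or because the effect lies in milder events.

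**Cost.** Wording and one further run of each algorithm; no new data collection and no change to randomisation. Care setting is normally recorded on claims, which should be confirmed for both trials' sources. The restricted version will have fewer events and wider intervals, and it omits milder events managed as outpatients, which is why the all-claims version stays.
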